### 12.2 Termination procedure

If the principal investigator or sub-investigator finds that a subject meets the termination criteria, this will be explained to the subject, the subject's participation in the clinical trial will be terminated, and appropriate measures will be taken. If a subject is judged to be ineligible at the time of registration, it is not necessary to create a case report form, and enrollment in the clinical trial will be ended without going through termination. When a subject requests clinical trial termination, the subject's rights should be fully respected and appropriate efforts should be made to confirm the reason.

1. Termination procedure prior to taking the investigational drug

If the clinical trial is terminated before the subject has taken the investigational drug, the principal investigator or sub-investigator should enter the termination date (the date on which the termination was determined) and the reason for termination in the case report form. In addition, unused investigational drugs will be collected at the time of the subject's visit.

2. Termination procedure after taking investigational drug

Except when the cooperation of the subjects is not obtained, the administration status of the investigational drug (during the administration period) and the occurrence status of adverse events are investigated. Tests and evaluations specified at the time of termination are performed. The principal investigator and others fill in the termination date (the date when the termination was judged) and the reason for the termination in the case report form. If termination is performed during the administration period, the remaining drug and the opened empty box will be collected at the time of the subject's visit.

The principal investigator or sub-investigator confirms the presence or absence of an adverse event. If an adverse event is found, the principal investigator or sub-investigator carries out a follow-up survey as a general rule.

clinical trial protocol 番号 : YCU-21001

### 13 Statistical analysis

#### 13.1 Target number of cases

28 cases (WY-8678 4 mg group: 14 cases; 8 mg group: 14 cases)

##### 【Setting basis】

As described in the setting basis of "9.5 Primary endpoint", the odds that the subject whose liver fat content changes from baseline  $\leq -3.46\%$  are truly histological responders are approximately 4.3 times the false positives. In this cutoff value setting, the true positive probability is 0.59 and the false positive probability is 0.25, and the following relationship holds. Therefore, when the probability of existence of a true histological responder is zero, the probability that the change in liver fat content from baseline  $\leq -3.46\%$  is 0.25.

$$\theta = (a - b)q + b = (0.59 - 0.25)q + 0.25$$

$\theta$ : Probability that the amount of change in liver fat content from baseline  $\leq -3.46\%$

q: Probability of existence of a true histological responder

a: True positive probability

b: False positive probability

This trial is designed to explore the minimal potential for efficacy in planning a placebo-controlled study in the next phase. The possibility that the probability of existence of a true histological responder is greater than zero can be examined by non-invasive means by showing that the proportion of subjects with a change in liver fat content from baseline  $\leq -3.46\%$  is  $> 0.25$ . Therefore, assuming that a binomial distribution is followed for the event in which the change in liver fat content from baseline  $\leq -3.46\%$ , we decided to set a sample size that can reject the null hypothesis  $H_0: \theta \leq 0.25$  by a one-sided test at the 5% level. As a concrete alternative hypothesis for setting the power, we assume  $H_0: \theta = \theta_1 = 0.5$ , which corresponds to the existence probability of 0.75 for a true histological responder. The sample size required to obtain 80% power was calculated to be 28 cases.

In this study, dose groups of 4 mg and 8 mg were set. The main concern is the total active drug administration cases. Half of the required sample size was assigned to each dose group.

#### 13.2 Analysis set

The analysis set is defined as follows and is determined before fixing the data for each case.

##### 1. Full Analysis Set (FAS)

Of all the randomized cases, the group excludes the cases that correspond to the items shown below.

- (1) Cases of serious clinical trial protocol violations (violations of consent acquisition, serious violations of clinical trial procedures, etc.).
- (2) Cases in which the investigational drug has never been administered.
- (3) Cases in which no endpoints related to efficacy have been measured.

##### 2. Per Protocol Set (PPS; analysis set conforming to clinical trial protocol)

A population of FAS excluding cases with clinical trial protocol violations, such as ex post facto findings of inclusion criteria violations or use of drugs or treatments whose concomitant use is prohibited.

##### 3. Safety Analysis Set (SAS)

Group of cases in which the investigational drug was administered, even once.

#### 13.2.1 Efficacy analysis set

The main analysis set for efficacy evaluation is the FAS.

clinical trial protocol 番号 : YCU-21001

### 13.2.2 Safety analysis set

The main analysis set for safety evaluation is the safety analysis set (SAS).

### 13.3 Data handling

As a general rule, missing data and outliers are not supplemented or excluded, and are used as they are. However, if there are cases that require special consideration before the data is fixed, the handling will be decided by the case review committee.

### 13.4 Statistical analysis protocol

The outline of the protocol is detailed below. Details of the statistical analysis method are described in the separately created statistical analysis protocol. If there is a change from the original analysis plan, it is described in this plan, statistical analysis protocol, or general report.

#### 13.4.1 Analysis of primary endpoint

The main analysis is conducted on the FAS. A point estimate is calculated for the proportion of subjects whose "liver fat content (%) measured by MRI-PDFF at 16 weeks decreased by 3.46% or more from baseline", and a 90% Clopper-Pearson confidence interval is created for it. The following hypothesis test is then performed. If the lower limit of the 90% Clopper-Pearson confidence interval is  $> 0.25$ , we reject the null hypothesis  $H_0: \theta \geq 0.25$  at the 5% level and conclude that  $\theta < 0.25$  (binomial test). Here,  $\theta$  is the probability that the amount of change in liver fat content from baseline  $\leq -3.46\%$ .

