Major statistical methods	
Analysis set
 
 
1. Efficacy analysis set The main analysis set for efficacy evaluation is the full analysis set (FAS).
 
2. Safety analysis set The main analysis set for safety evaluation is the safety analysis set (SAS).
 
 
Data handling
 
As a general rule, missing and outliers are not supplemented or excluded, and are used as they are. However, if there are cases that require special consideration before the data is fixed, the handling will be decided by the case review committee. In addition, the final treatment of variables related to timing in the analysis is specified in the statistical analysis protocol.
 
Statistical analysis protocol
 
 
1. Primary endpoint The main analysis is for the FAS. A point estimate was calculated for the proportion of subjects whose "liver fat content (%) measured by MRI-PDFF at 16 weeks decreased by 3.46% or more from baseline", and a 90% Clopper-Pearson confidence interval is created for it. The following hypothesis test is then performed: If the lower limit of the 90% Clopper-Pearson confidence interval is <math>> 0.25</math>, we reject the null hypothesis <math>H_0: \theta \geq 0.25</math> at the 5% level and conclude that <math>\theta < 0.25</math> (binomial test). Here, <math>\theta</math> is the probability that the amount of change in liver fat content from baseline <math>\leq -3.46\%</math>.
 
2. Secondary endpoints For each secondary endpoint, each group is summarized using descriptive statistics and parallel-group comparison is performed using t-test.
 
 
Significance level and confidence coefficient
 
This clinical trial is exploratory and does not set any specific statistical hypothesis. When performing a test or interval estimation for exploratory purposes, the significance level is 5% (total of upper and lower) and the confidence coefficient is 95%. Multiplicity is not considered for the test and the interpretation of confidence intervals.

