### 13.5 Significance level and confidence coefficient

When performing a test or interval estimation, the significance level is 5% (two-sided) and the confidence coefficient is 95% unless otherwise specified. Multiplicity is not considered for the test and the interpretation of confidence intervals.

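### The primary decision rule in 13.4.1 and the Summary states the null hypothesis and the conclusion the wrong way round, contrary to 13.1

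*Protocol*

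**What the plan says.** **Protocol 13.4.1** takes the full analysis set, estimates the responder proportion with a 90% Clopper-Pearson interval and then gives a decision rule. The condition is "If the lower limit of the 90% Clopper-Pearson confidence interval is $> 0.25". The consequence is "we reject the null hypothesis $H_0: \theta \geq 0.25$ at the 5% level and conclude that $\theta < 0.25$ (binomial test". The section defines the parameter: θ "is the probability that the amount of change in liver fat content from baseline $\leq -3.46" percent. θ is therefore the probability of response, and larger is better.

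**The Summary**, under the primary endpoint, repeats the same condition with the same consequence: "we reject the null hypothesis H_0: \theta \geq 0.25 at the 5% level and conclude that \theta < 0.25 (binomial test".

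**Protocol 13.1**, in the basis for the sample size, goes the other way. The trial is sized so that it can "reject the null hypothesis $H_0: \theta \leq 0.25$ by a one-sided test at the 5% level", and the stated purpose is to show that the responder proportion is greater than 0.25.

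**On levels**, 13.5 says that "the significance level is 5% (two-sided) and the confidence coefficient is 95% unless otherwise specified". The Summary adds that "This clinical trial is exploratory and does not set any specific statistical hypothesis".

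**The concern.** The trigger, the null hypothesis and the conclusion in 13.4.1 cannot all stand. If the lower limit is above 0.25, the whole interval lies above 0.25. That is evidence against θ ≤ 0.25, and it cannot reject θ ≥ 0.25 or support θ < 0.25. Read literally, the outcome the investigators hope for is given the label of the outcome they hope to rule out.

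This is the only decision rule the protocol sets for the primary endpoint, and 13.1 says the result is meant to inform a placebo-controlled study. A statistical analysis plan that copies 13.4.1 inherits the error. One that follows 13.1 contradicts 13.4.1 and the Summary. The direction of the primary test should be settled in the protocol before the data are fixed, not by interpretation afterwards.

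**Working it through.** **Inputs.** From 13.1: n = 28 (both dose groups pooled, 14 + 14), reference value 0.25, one-sided 5%, 80% power, and θ1 = 0.5 for power (printed there with the label H0, although it is the alternative). From 13.4.1: a 90% Clopper-Pearson interval with the lower limit compared with 0.25. X is the number of responders.

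**Formulas.**
- Upper tail: P(X ≥ c | n, θ) = Σ from k = c to n of C(n,k) θ^k (1 − θ)^(n − k).
- 90% Clopper-Pearson limits at x responders: lower = 5% quantile of Beta(x, n − x + 1); upper = 95% quantile of Beta(x + 1, n − x).
- The lower limit exceeds 0.25 exactly when P(X ≥ x | n, 0.25) < 0.05. The lower-limit trigger is therefore the one-sided 5% exact test of H0: θ ≤ 0.25.

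**Step 1: reproduce the plan's sample size, using H0: θ ≤ 0.25.** The cut-off c is the smallest count with P(X ≥ c | n, 0.25) ≤ 0.05.

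| n | c | alpha at θ = 0.25 | power at θ = 0.5 |
|---|---|---|---|
| 26 | 11 | 0.0401 | 0.8365 |
| 27 | 12 | 0.0216 | 0.7790 |
| 28 | 12 | 0.0294 | 0.8275 |
| 29 | 12 | 0.0390 | 0.8675 |
| 30 | 13 | 0.0216 | 0.8192 |

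Exact power moves in a saw-tooth. It falls below 80% at n = 27 and stays above 80% at every n checked from 28 to 33. The figure of 28 is reproduced under the direction in 13.1.

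**Step 2: when does the 13.4.1 trigger fire at n = 28?**
- 11/28: lower limit 0.238, does not fire.
- 12/28: interval 0.269 to 0.600, fires.

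The rule is X ≥ 12, the same cut-off as in Step 1. Trigger and sample size agree with each other and with H0: θ ≤ 0.25.

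**Step 3: what would a test of the printed null need?** Rejecting H0: θ ≥ 0.25 requires the upper limit to be below 0.25.
- 2/28: upper limit 0.208; P(X ≤ 2 | 28, 0.25) = 0.0166, rejects.
- 3/28: upper limit 0.254, does not reject.

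That rule is X ≤ 2. It has no outcome in common with X ≥ 12.

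**Step 4: the printed rule taken as a test of the printed null.** The chance of rejecting θ ≥ 0.25 at values where it is true is P(X ≥ 12 | 28, θ):

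| true θ | probability of concluding θ < 0.25 |
|---|---|
| 0.25 | 0.0294 |
| 0.30 | 0.1028 |
| 0.50 | 0.8275 |
| 0.75 | 0.9999 |

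As a test of the null it names, the rule is not a 5% test: the wrong conclusion becomes more likely as the response rate rises. As a test of H0: θ ≤ 0.25 it works as designed.

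**The case against.** The strongest reply is that the intent is plain. Section 13.1 gives the aim and the null in the right direction, the numerical trigger is correct, and an analyst who sees an interval lying wholly above 0.25 will not report θ < 0.25. Sample size, cut-off, alpha and power do not change with the correction. All of this stands, and it limits the practical weight. It does not make the text acceptable. The null and the conclusion are both reversed, consistently with each other, in two separate places, so this is neither one stray sign nor plausibly a fault of text extraction.

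Three stronger readings are tempting, and the documents do not support them.

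- *A successful trial would formally be reported as a failure.* The printed rule contradicts itself and 13.1; it does not dictate that report. The trigger and the stated aim both point to θ > 0.25.
- *The significance level is also in conflict, because 13.5 sets two-sided 5% and 95%.* A 95% interval would move the cut-off to 13 of 28 and reduce power to 71.4%, with 12/28 failing (95% lower limit 0.245). But 13.5 yields wherever something else is specified, and 13.4.1 and the Summary both name a 90% interval for the primary endpoint. Its lower limit is the one-sided 5% test of 13.1. The Summary's own 95% sentence lacks that exception, but it concerns testing done for exploratory purposes and stands beside the explicit 90% interval. No section prescribes 95% for the primary endpoint.
- *The trial's only confirmatory rule is wrong.* The protocol describes an exploratory proof-of-concept study. This is its primary decision rule, not a confirmatory one.

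**Conclusion.** The point holds as a wording error in the primary decision rule, made in both 13.4.1 and the Summary and contradicted by 13.1. At n = 28 it attaches the label θ < 0.25 to every outcome with 12 or more responders, which has probability 82.75% if θ = 0.5. The method itself is sound: the lower-limit trigger, n = 28, attained alpha of 0.0294 and power of 82.75% all belong to H0: θ ≤ 0.25 and need no change.

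The figures assume 28 analysed patients with a binomial responder count pooled over the two doses, as 13.1 does. A different number in the full analysis set would move the cut-off but not the direction of the error.

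The Summary's statement that no specific hypothesis is set sits badly beside the test it describes. That is a minor drafting inconsistency and adds nothing to the size of the main point.

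**What to change.** In 13.4.1 and in the Summary, replace the rule with: *If the lower limit of the two-sided 90% Clopper-Pearson interval exceeds 0.25, H0: θ ≤ 0.25 is rejected at the one-sided 5% level and θ > 0.25 is concluded.*

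As a minor consequential edit, make the Summary's no-hypothesis statement except the primary endpoint. Section 13.5 needs no change.

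The cost is a text amendment, with no effect on conduct, threshold, sample size, alpha or power. It should be made before the data are fixed, and the statistical analysis plan should carry the same wording.

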#### 13.4.2 Analysis of secondary endpoints

For each secondary endpoint, each group is summarized using descriptive statistics and parallel-group comparison is performed using t-test.

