## 3 Purpose of clinical trial

### 3.1 Purpose

We will investigate the efficacy and safety of 4 mg/day and 8 mg/day of WY-8678 (guanabenz acetate) in NAFLD/NASH patients with hypertension.

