#### 【Setting basis】

To determine drug efficacy two approved dose groups are set (4 mg/day and 8 mg/day). The efficacy of each group is evaluated instead of a parallel-group comparison.

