### 9.6 Secondary endpoints

clinical trial protocol 番号 : YCU-21001

1) Amount of change and rate of change from baseline in the measured values at 16 weeks were determined. The rate of change is defined as (value at 16 weeks - baseline value) / (baseline value).

The following items were measured:

- Percentage of subjects where the liver fat content (%) measured by MRI-PDFF at 16 weeks decreased by  $\geq 3.46\%$  from baseline for the 4 mg and 8 mg groups
- Amount of change and rate of change in liver fat content measured by MRI-PDFF
- Rate of change in ALT, AST, and  $\gamma$ -GTP
- Rate of change in weight
- Rate of change in blood lipids (chylomicron cholesterol, chylomicron triglyceride, lipoprotein cholesterol, LDL triglyceride, VLDL cholesterol, VLDL triglyceride, free cholesterol, apoprotein A1, apoprotein B, adipsin, free fatty acid)
- Rate of change in insulin resistance (HOMA-IR)
- Rate of change in liver hardness (MRE)
- Rate of change of fibrosis markers (ELF score, Fibrosis-4 [FIB-4])

2) Search for new markers related to liver disease and obesity metabolic disease

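### The design rationale sets aside a comparison of the two doses, yet a 4 mg versus 8 mg t-test is the only inference fixed for the secondary endpoints, including the binary responder percentage

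*Protocol*

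**What the plan says.** All references are to the protocol.

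- **Purpose (3.1):** "We will investigate the efficacy and safety of 4 mg/day and 8 mg/day of WY-8678", in patients with fatty liver disease and hypertension. Each dose is named.
- **Design rationale (setting basis under 8.1.2):** "The efficacy of each group is evaluated instead of a parallel-group comparison".
- **Secondary endpoints (9.6):** the list includes the percentage of subjects whose liver fat falls by at least 3.46%, "from baseline for the 4 mg and 8 mg groups". It also includes the amount and rate of change in liver fat, and rates of change in liver enzymes, weight, lipids, HOMA-IR, MRE and fibrosis markers.
- **Secondary analysis (13.4.2, repeated in the Summary under the statistical methods):** for each of these endpoints, "each group is summarized using descriptive statistics and parallel-group comparison is performed using t-test".
- **Subgroups (13.4.4):** a further comparison between the dose groups is planned for liver fat, ALT, AST, gamma-GTP and MRE, by presence or absence of the susceptibility genes.
- **Primary analysis (13.4.1) and sample size (13.1):** a 90% Clopper-Pearson interval and binomial test on the responder proportion, with no split by dose. The setting basis under 13.1 says "The main concern is the total active drug administration cases".

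**The concern.** The design section and the analysis section cannot both be followed. Under 8.1.2 the doses are to be judged one at a time. Under 13.4.2 the only inferential step is to compare them, and no interval or test is fixed for a single dose.

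This matters because both arms receive active drug. If both doses reduce liver fat equally, the contrast is null. If neither works, it is also null. The comparison therefore does not address the purpose in 3.1, which concerns efficacy at each dose.

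The wording also sends a yes/no variable, the per-dose responder percentage, to a t-test. The primary analysis treats the same variable with an exact binomial method.

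**Working it through.** **Inputs from the protocol.** 28 subjects, 14 per dose (13.1). Null responder probability 0.25, alternative 0.50, "by a one-sided test at the 5% level", 80% power (setting basis under 13.1). Two-sided 5% and 95% confidence for other tests and intervals (13.5). No adjustment factor at allocation (6.2).

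**Assumptions not in the protocol.** Correlation rho between baseline and week 16 of 0.3, 0.5 or 0.7; equal variances at the two times; standardised dose differences d of 0.5, 0.8 and 1.0.

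**1. The protocol's own figure.** The rule is the smallest r with P(X ≥ r | n, 0.25) ≤ 0.05. At n = 28, r = 12. The exact level is 0.029, and power at 0.50 is P(X ≥ 12 | 28, 0.50) = 0.828. The 90% Clopper-Pearson lower limit for 12/28 is 0.269, above 0.25. The 28 reproduces, for the pooled group.

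**2. The same rule within one dose.** At n = 14, r = 7. The exact level is 0.038 and power at 0.50 is 0.605. For 7/14 the exact interval is 0.264 to 0.736 at 90% and 0.230 to 0.770 at 95%.

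**3. Mean change within one dose.** The half-width of a 95% interval is t(0.975, 13)/√14 = 2.160/3.742 = 0.58 SD of the change.

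**4. The t-test that is planned.** With 14 per arm, df = 26 and noncentrality d × √(14/2) = 2.646 × d. Two-sided 5% power:

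| d (SD units) | Power |
|---|---|
| 0.5 | 0.25 |
| 0.8 | 0.53 |
| 1.0 | 0.72 |
| 1.10 | 0.80 |

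Between two doses of the same drug, a difference of 1.1 SD is a large requirement.

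**5. Baseline adjustment, for the amount of change in liver fat.** The variance of a change score is proportional to 2(1 − rho), and that of the baseline-adjusted estimate to 1 − rho². The ratio, adjusted to unadjusted, is (1 − rho²)/[2(1 − rho)] = (1 + rho)/2:

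- rho = 0.3: 1.3/2 = 0.65
- rho = 0.5: 1.5/2 = 0.75
- rho = 0.7: 1.7/2 = 0.85

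The formula describes an absolute change. It does not describe a rate of change, which is already divided by baseline. Most of the items listed in 9.6 are rates.

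**The case against.** The best defence is that pooling is deliberate. Section 13.1 makes all treated subjects the main concern and sizes the trial for one pooled test. The study is a proof of concept, with the appropriate dose left to a Phase IIb study (8.1.3). Power of 60% per dose explains why no per-dose test was planned. The Summary calls the trial exploratory, and the Summary and 13.5 both disclaim multiplicity control. Section 13.4 describes itself as an outline and leaves details to a separate analysis plan. Nothing says that a non-significant contrast would be read as lack of efficacy.

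Most of this stands. It protects the primary analysis and argues against formal per-dose testing. It does not remove the contradiction: 13.4.2 has already chosen a method, and an analysis plan that follows it departs from 8.1.2.

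Three stronger readings are tempting, and the protocol does not support them:

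- *The analysis only compares the groups.* The same sentence in 13.4.2 summarises each group, and the per-dose responder percentage is a listed endpoint. What is absent is a fixed interval or test for each dose, and the separate analysis plan may supply one.
- *Baseline is ignored.* The endpoints in 9.6 are changes and rates of change from baseline. Only a baseline covariate is missing. In a randomised comparison that costs precision and leaves chance imbalance uncorrected; it is not a bias.
- *Skewed markers invalidate the t-test.* The protocol gives no distributional data, and a log-scale analysis can be left to the analysis plan.

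**Conclusion.** The point holds as a contradiction about secondary analyses. Section 8.1.2 disclaims the dose comparison. Section 13.4.2, the Summary and 13.4.4 prescribe it, and for the secondary endpoints it is the only inference fixed. It cannot show whether either dose works, it reaches 80% power only at about 1.1 SD, and its method does not suit the responder percentage.

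The primary conclusion is untouched, and the 28 subjects are correctly derived for it. Per-dose estimates will be imprecise whatever is done (0.26 to 0.74 at 7/14, 90% interval), so they serve as estimates and not as tests.

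The benefit of baseline adjustment, a variance of 0.65 to 0.85 times the unadjusted one, rests on the assumed correlations and equal variances. It applies to the absolute change in liver fat only. This is worth correcting, as an improvement to exploratory analyses.

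**What to change.** 1. Reconcile the setting basis under 8.1.2 with 13.4.2, the matching Summary text and 13.4.4, so that all four say the same about comparing doses.
2. In 13.4.2, report for each dose and for the pooled group the mean change with a 95% confidence interval, and the responder percentage with a Clopper-Pearson interval at a stated level (90% to match the primary analysis, or the 95% default of 13.5). State that precision per dose is low.
3. If the dose contrast is kept, label it exploratory where it is specified. For responders, replace the t-test with a risk difference and an exact confidence interval. For continuous items, adjust for the baseline value by ANCOVA, described as a gain in precision.

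The cost is a protocol wording change and minor programming. No new data, visits or subjects are needed.
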